### 7.1.5. Dose Adjustment/Discontinuation Pharmacokinetic Criteria

The exposures observed in animal toxicology studies will be used to guide dose escalation. Systemic exposures in the human participants in this study may exceed the systemic NOAEL animal exposures from 14-day GLP toxicology studies if the doses administered in the study are safe and well tolerated.

For Part 1, the need to dose escalate will be evaluated if no meaningful increase in exposure is observed with an increase in dose (i.e., a plateau in exposures is reached).

## 7.2. Study Stopping Criteria

In the event of any of the following, ongoing dosing will be halted and no new participants will be dosed at this dose level. A safety review will be undertaken; following this review an additional cohort may be enrolled at a lower dose level.

- An SAE that is related to GSK3882347 in one or more participants on active treatment.
- Two similar AEs of moderate intensity in 2 or more participants.
- Two AEs of severe intensity (but not necessarily similar) in 2 or more participants.
- Finally, if a sentinel participant receiving GSK3882347 meets any of these clinical stopping criteria, the rest of the Period (SAD) or Cohort (MAD) will not be dose and further dose escalation will not occur (see Section 7).

Dosing at the current (higher or lower) dose may resume only following approval of a substantial amendment by the MHRA as well as the ethics committee.

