**Table 3 Part 2 – 7-Day Repeat Dose Escalation (Days 1 and 7)**

Procedure	Study Days													Notes
	1 and 7													
	-1	Predose	0	0.25	0.5	1	1.5	2	4	6	8	12	16	Hours relative to study intervention
Inclusion and exclusion criteria	X													Recheck clinical status before randomization and/or 1 st dose of study treatment
Brief physical examination	X													
Urine Drug, Smoke Breathalyzer/Alcohol Breath Tests	X													Additional testing may be performed at other timepoints
β-hCG pregnancy test	X													Pregnancy test as appropriate
Admission to clinical unit	X													
Randomization		X												Randomization will occur before first dose on Day 1 only.
Administration of study intervention			X											
AE Review			X	←	Continuous review									
SAE Review				←	Continuous review									Serious AEs will be collected from the signing of informed consent.
Ad hoc COVID-19 testing based on clinical presentation and site procedures				←	Continuous review									
Concomitant medication review			X	←	Continuous review									

Procedure	Study Days													Notes
	1 and 7													
	-1	Predose	0	0.25	0.5	1	1.5	2	4	6	8	12	16	Hours relative to study intervention
Vital signs (BP, HR, tympanic temperature, respiration rate)	X	X*				X		X	X	X	X			Vital signs will be obtained within 1 hour of pre-dose and at 1, 2, 4, 6, 8, 12 and 24 hours after study administration on Days 1 and 7.  *Triplicate readings of blood pressure and pulse rate will be taken pre-dose and averaged on Days 1 and 7.  Single measurements will be obtained at all other timepoints.  Timings will be reviewed as cohorts progress and may be adjusted to ensure appropriate measurements relative to peak concentrations for subsequent cohorts.

Procedure	Study Days													Notes	
	1 and 7														
	-1	Predose	0	0.25	0.5	1	1.5	2	4	6	8	12	16		
12-lead safety electrocardiogram	X	X*				X		X	X	X	X	X		*Triplicate 12-lead safety ECGs will be obtained no more than 15 minutes apart within 1-hour pre-dose on Days 1 and 7.  Single 12-lead safety ECGs will be obtained at 1, 2, 4, 6, 8, 12 and 24 hours after study administration on Days 1 and 7.	

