#### 7.1.1. Gastrointestinal Events (diarrhea or colitis)

[figure not shown]
Grade	Diarrhea	Management	Follow-up
Mild (Grade 1)  An event that is easily tolerated by the participant, causing minimal discomfort and not interfering with everyday activities	Increase of <4 stools per day over Baseline	
 
Administer antidiarrheal and symptomatic treatment as appropriate
 
Discuss participant continuation in the trial with Sponsor/Medical Monitor
 
	
Symptoms resolve to baseline within 3 days:
 
 
Provide close follow-up to evaluate for increased severity.
 
 
Symptoms ongoing > 3 days:
 
 
Consider following algorithm for Grade 2 events
 

Moderate (Grade 2)  An event that causes sufficient discomfort and interferes with normal everyday activities	Increase of 4 - 6 stools per day over Baseline	
 
Interrupt study drug(s)
 
Administer antidiarrheal and symptomatic treatment
 
Investigate etiology; consider consulting GI service
 
Discuss participant continuation in the trial with Sponsor/Medical Monitor
 
	
Symptoms resolve to ≤ Grade 1 or baseline within 7 days:
 
 
Continue follow-up and evaluate for any increased severity.
 
 
Symptoms ongoing > 7 days, blood or mucus in stool, or ulceration/bleeding on endoscopy:

Grade	Diarrhea	Management	Follow-up
			
 
Consider following algorithm for Grade 3 events
 

Severe (Grade 3-4) An event that prevents normal everyday activities	Grade 3: Increase of $\geq 7$ stools per day over Baseline; incontinence; hospitalisation indicated  Grade 4: life-threatening consequences; urgent intervention indicated	
 
Discontinue study drug(s)
 
Consult GI service
 
Discuss participant continuation in the trial with Sponsor/Medical Monitor
 
	
Symptoms ongoing:
 
 
Continue follow up of participant
 
Discuss further management with GI consultant and Sponsor/Medical Monitor
 

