### 7.1.2. Liver Chemistry Stopping Criteria

Study intervention will be discontinued for a participant if liver chemistry stopping criteria are met:

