### 7.1.3. QTc Stopping Criteria

- The Fridericia QT correction formula (QTcF) *must* be used for *each individual participant* to determine eligibility for and discontinuation from the study. This formula may not be changed or substituted once the participant has been enrolled. Safety ECGs and other non-protocol specified ECGs are an exception.
- The QTc should be based on averaged QTc values of triplicate electrocardiograms obtained over a brief (e.g., 15 minute) recording period.
- A participant that meets either bulleted criterion below will be withdrawn from the study.
  - QTcF > 500msec,
  - Change from baseline: QTcF >60msec

See Section 1.3 for data to be collected at the time of study intervention discontinuation and follow-up and for any further evaluations that need to be completed.

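### In Part 2, Section 7.2 requires no cohort-level pause when two or more active participants meet the same isolated-ALT or QTc stop

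*Protocol*

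**What the plan says.** **Cohort level (Protocol 7.2).** "In the event of any of the following, ongoing dosing will be halted and no new participants will be dosed at this dose level". The listed triggers are:
- one or more SAEs related to GSK3882347 on active treatment;
- two similar AEs of moderate intensity in two or more participants;
- two severe AEs, similar or not, in two or more participants.

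A further bullet stops the rest of the period or cohort, and further escalation, "if a sentinel participant receiving GSK3882347 meets any of these clinical stopping criteria". It ends with a general pointer to Section 7. After a halt, dosing "may resume only following approval of a substantial amendment by the MHRA as well as the ethics committee".

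**Participant level.**
- Liver (7.1.2, with Appendix 6): "Study intervention will be discontinued for a participant if liver chemistry stopping criteria are met". The threshold is ALT at least 3 times ULN. The event becomes a mandatory SAE report only with raised bilirubin or INR.
- QTc (7.1.3): "A participant that meets either bulleted criterion below will be withdrawn from the study". The criteria are QTcF above 500 msec or more than 60 msec over baseline, and "The QTc should be based on averaged QTc values of triplicate electrocardiograms obtained over a brief" recording period.
- Gastrointestinal (7.1.1): Grade 2 is defined as "An event that causes sufficient discomfort and interferes with normal everyday activities", which is how Section 10.3.3 defines moderate intensity.

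**Review and reporting.** Liver stops go to the sponsor within 24 hours (Appendix 6). Safety concerns are discussed with the sponsor at once (Section 8). The DEC has ongoing monitoring and may review unblinded data (9.5.1). Before the rest of a cohort is dosed, the Principal Investigator and Medical Monitor review the sentinels' safety data, including ECGs and laboratory results (1.1 Synopsis; also 2.3.1).

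**The concern.** Two of the individual stops are objective: a laboratory value and an ECG interval. The AE-based cohort triggers depend on an intensity rating. The gastrointestinal stop feeds those triggers by definition, because its grades use the wording of the intensity scale. The liver and QTc stops have no such link.

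This matters in Part 2, where seven non-sentinel active participants are dosed in parallel for 7 days. Two similar moderate AEs of any kind, related or not, force a halt. Two active participants taken off drug for the same ALT or QTcF finding force nothing unless the investigator also rates the events moderate or severe, or one is a related SAE. In a first-in-human repeat-dose cohort, a repeated objective signal on active drug should prompt a look at the whole dose level before the others take their next dose.

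**Working it through.** The plan states no figure on this point, so the main check is of the text.

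**1. Can an isolated ALT or QTc stop reach a 7.2 trigger?**
- *Related SAE.* ALT alone is not made an SAE; Appendix 6 requires raised bilirubin or INR as well. 7.1.3 does not make a QTc stop an SAE. The investigator may still judge either to be a related SAE.
- *Two similar moderate or two severe AEs.* A laboratory or ECG abnormality is an AE if the investigator considers it clinically significant (10.3.1; for laboratory changes also 8.2.5). Intensity is then graded by discomfort and interference with everyday activities (10.3.3), with no laboratory or ECG threshold. A symptom-free finding can be rated mild.
- *Result.* None of the three triggers names either stop, and every route into 7.2 runs through judgement.

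**2. The sentinel bullet.** Each cohort has one active sentinel. The second and third triggers need two participants, so read literally that sentinel alone can meet only the related-SAE trigger. The pointer to Section 7 may be meant to bring in 7.1.2 and 7.1.3, but it does not say so.

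**3. Exposure at stake (ALT, Part 2).** Inputs: seven non-sentinel active participants (1.1 Synopsis), 7 daily doses, and chemistry on what appear to be Days 3 to 6 (Table 4, whose columns are broken in the text available). Assumptions: two participants stop on the same Day d, and the result is back before the next dose. Further doses scheduled for the other five = 5 × (7 − d):

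| Day of stop | Further active doses |
|---|---|
| 3 | 5 × 4 = 20 |
| 4 | 5 × 3 = 15 |
| 5 | 5 × 2 = 10 |
| 6 | 5 × 1 = 5 |

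The active sentinel adds none. That participant's Day 7 dose is at 144 h and the others start at 120 h, so it falls on their Day (144 − 120)/24 + 1 = 2.

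These counts do not carry over to QTc. Table 3 says: "Triplicate 12-lead safety ECGs will be obtained no more than 15 minutes apart within 1-hour pre-dose on Days 1 and 7". No other triplicates are scheduled after dosing starts, so without an unscheduled triplicate a QTc stop would be established only around the Day 7 dose.

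**4. How often the proposed pause would act.** The document gives no event rate, so p is assumed, for one criterion and with independent participants. P(at least 2 of n) = 1 − (1 − p)^n − n·p·(1 − p)^(n−1). For n = 8 and p = 0.05: 1 − 0.6634 − 0.2793 = 0.0572 before rounding of the terms.

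| Assumed p | 8 active | 7 non-sentinel active |
|---|---|---|
| 1% | 0.3% | 0.2% |
| 5% | 5.7% | 4.4% |
| 10% | 19% | 15% |

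**5. Cost of making one sentinel stop an automatic 7.2 halt.** P(at least one active-sentinel stop over four Part 2 levels) = 1 − (1 − p)^4 = 3.9%, 18.5% and 34.4% at 1%, 5% and 10%. Each such event would end escalation until the MHRA and the ethics committee approved a substantial amendment.

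**The case against.** The strongest reply is that controls already exist. Clinically significant ALT or ECG findings are AEs, every AE is rated, and two similar moderate ones halt dosing whether or not they are related. ALT with raised bilirubin or INR is already an SAE. Sponsor physicians have access to unblinded data for dose escalation (6.3), and liver stops reach the sponsor within a day. The gap therefore opens only if two participants are compulsorily stopped for the same finding, the investigator rates the events below moderate, and nobody uses the available discretion. The only product risk listed in 2.3.2 is gastrointestinal, which 7.2 captures, and 4.2 reports no preclinical cardiovascular risk. The Dose Escalation Plan may contain a rule.

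All of this stands and lowers the priority. It does not close the gap, because each of the controls seen permits a pause without requiring one, and the scheduled DEC decision governs the next dose level rather than dosing under way.

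A reader might go further and infer that an ALT or QTc stop in the active sentinel would let the rest of the cohort be dosed unchecked. The documents do not support that: the safety review before the remaining eight are dosed expressly covers ECGs and laboratory results. Nor do they support making one such sentinel stop an automatic 7.2 halt. The sentinel bullet also covers Part 1, and a single isolated finding would then carry a heavier consequence than two in the main group.

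**Conclusion.** The point holds as a cheap improvement of low-to-modest priority, for Part 2 only. Section 7.2 does not require a pause when two or more active participants meet the same isolated-ALT or QTc stop, because its AE triggers depend on a rating that symptom-free findings need not reach. The sentinel wording is ambiguous, but the existing review limits its practical effect.

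The exposure at stake is 5 to 20 further scheduled active doses in the ALT case. That rests on both stops falling on the same day, results returning before the next dose, and the apparent chemistry schedule in Table 4; 20 is the Day 3 extreme. No comparable count is available for QTc. The pause frequencies are illustrative, since no event rate is given.

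It would be wrong to read this as saying that dosing would in fact continue, or that a hepatic or cardiac hazard has been identified. The documents show neither.

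**What to change.** Add to 7.2:
- If two or more participants on active treatment at a Part 2 dose level meet the same criterion (both 7.1.2, or both 7.1.3 confirmed on triplicate ECG), whatever the AE intensity, dosing at that level is paused for an ad hoc DEC review, with the unblinded members confirming treatment.
- This pause is outside the sentence requiring a substantial amendment to resume, unless the DEC makes it a 7.2 halt.

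If the sentinel bullet is clarified too, say that an active sentinel meeting 7.1.2 or 7.1.3 holds dosing of the rest of the cohort pending the same DEC review. It should not automatically end escalation. Mirror the wording in the Dose Escalation Plan, after checking whether that plan already has a rule.

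The cost is two or three sentences, using the existing DEC and sponsor staff who are already unblinded. The downsides are occasional pauses (illustratively 5.7% per level with eight active at an assumed 5% rate), some lost steady-state PK data if a pause breaks the 7-day dosing, and unscheduled triplicate ECGs to confirm a QTc stop, which 7.1.3 already implies.

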## Part 2: Repeat Dose Escalation in Healthy Adult Participants

Part 2 consists of a maximum of four ascending repeat-dose cohorts (Cohorts 3 to 6), each with 10 participants who will receive a single oral dose of GSK3882347 or placebo for 7 days. The earliest point at which Part 2 of the study will be initiated is once the single dose safety and preliminary PK data at an exposure that exceeds the daily exposure predicted at steady state for the Part 2 planned starting dose of 50 mg is demonstrated in Part 1. The planned starting dose of GSK3882347 in Part 2 is 50 mg administered as once daily Days 1 to Day 7. The dose is planned to increase in subsequent cohorts to 150, 500 and 900 mg. The starting dose and maximum dose may be changed based on clinical safety, tolerability and PK findings in Part 1 or earlier doses in Part 2 and consideration of the area under the concentration-time curve (AUC) from time zero to 24 hours after dosing (AUC[0-24]) and maximum plasma concentration (Cmax) exposures based on the no-observed-adverse-effect-level (NOAEL).

Participants who meet the criteria for study entry will be assigned to the current dose level and randomized to receive GSK3882347 or placebo in a 4:1 ratio before administration of study intervention on Day 1 in Part 2. As a safety precaution, cohorts will be split into two sub-cohorts to allow sentinel dosing. At each dose level (Cohorts 3-6), the first two participants will receive either GSK3882347 or placebo (one active and one placebo). Dosing of the remaining eight participants (seven active and one placebo) in that cohort will occur at least 120 hours later based on review of the safety data (e.g. vital signs, ECGs, clinical laboratory results and adverse events) by the Principal Investigator and sponsor Medical Monitor from all sub-cohorts of sentinel participants. The 120 hour timeframe was selected on the basis of available preclinical data, as GSK3882347 is anticipated to have reached steady-state by 120 hours, however this duration may be increased or decreased based on emerging PK data.

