**Table 2      Part 1 - Single Dose Escalation and Food Effect**

Procedure	-1	Study Days																Notes
		Predose	0	0.25	0.5	1	1.5	2	4	6	8	12	16	24	32	48	72	96
Inclusion and exclusion criteria	X																	Hours relative to study intervention
Brief physical examination	X													X		X		X
Urine Drug, Smoke Breathalyzer/Alcohol Breath Tests	X																	Additional testing may be performed at other timepoints
β-hCG pregnancy test	X																	Pregnancy test as appropriate
Admission to clinical unit	X																	Participants to be admitted to the unit the day before dosing (Day -1) and remain in house until discharge
Randomization		X																Randomization will occur before first dose in Period 1
Administration of study intervention			X															No minimum time interval is required between the sentinels at each dose level. Approximately 15 minutes will be observed between the dosing of the remaining participants
AE Review			X	Continuous review														
SAE Review			←	Continuous review														Serious AEs will be collected from the signing of informed consent.

Procedure	-1	Study Days															Notes		
		Predose	0	0.25	0.5	1	1.5	2	4	6	8	12	16	24	32	48	72		
Ad hoc COVID-19 testing based on clinical presentations and site procedures		Continuous review															X	Sample collected upon discharge	
Concomitant medication review				X	Continuous review														
Vital signs (BP, HR, tympanic temperature, respiration rate)	X	X*				X		X	X	X	X		X		X	X	X	*Triplicate measurements of blood pressure and pulse rate will be obtained pre-dose and averaged.  Single measurements will be obtained at all other timepoints.  Timings will be reviewed as cohorts progress and may be adjusted to ensure appropriate measurements relative to peak drug concentrations for subsequent cohorts.	
12-lead safety electrocardiogram	X	X*				X		X	X	X	X		X					Triplicate 12-lead safety ECGs will be obtained no more than 15 minutes apart within 1-hour pre-dose and single measurements will be obtained at all other timepoints.	

Procedure	-1	Study Days															Notes		
		1																	
		Predose	0	0.25	0.5	1	1.5	2	4	6	8	12	16	24	32	48	72	96	

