### 7.1.4. Individual Stopping Criteria

- Any participant who experiences an SAE will be withdrawn from the study.
- Any participant who experiences an AE of moderate or severe intensity that is considered attributable to dosing with GSK3882347 will be withdrawn from the study.
- If a participant develops COVID-19 like symptoms during the course of the study the following actions should be taken:
  - During Part 1 (SAD portion of the study), participants who develop a high clinical index of suspicion for COVID-19 disease should be isolated and tested for COVID-19 in accordance with site procedures.
  - During Part 2 (MAD portion of the study), study treatment should be halted for any participants who develop a high clinical index of suspicion for COVID-19 disease; they should be isolated and tested for COVID-19 in accordance with site procedures.
  - In both cases, assessments should be continued as per the protocol during this period; withdrawal of participants from the study will be at the discretion of the Principal Investigator, but should first be discussed and agreed with the GSK Medical Monitor.

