### 9.5.1. Dose Escalation Committee (DEC)

A Dose Escalation Committee (DEC) will be responsible for ongoing monitoring during the study.

A DEC consisting of the following members including but not limited to the Principal Investigator, GSK Medical Monitor, GSK Clinical Scientist Lead, GSK Discovery Medicine Lead, GSK Pharmacokineticist, GSK Safety and Medical Governance Representative, GSK Statistician, GSK Study Delivery Lead and GSK Data Quality Lead will review available data from all participants in each cohort; and before initiating each new dose level in a minimum of four participants who received active treatment in the previous cohort in Part 1 and at least 7 days of repeat dosing in a minimum of five participants who received active treatment in the previous cohort in Part 2. Dose escalation may occur only after review of the following data:

- Part 1: Up to Day 2 (24 hours) post-dose for PK and Day 5 (96 hours) post-dose for safety
- Part 2: Up to Day 8 (24 hours post-Day 7) for safety and PK

The data may be reviewed in an unblinded fashion by the unblinded members of the DEC should a safety concern arise during the blinded review. These unblinded members will be defined within the Dose Escalation Plan.

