### 10.3.3. Recording and Follow-Up of AE and SAE

AE and SAE Recording

When an AE/SAE occurs, it is the responsibility of the investigator to review all documentation (e.g., hospital progress notes, laboratory, and diagnostics reports) related to the event.

The investigator will then record all relevant AE/SAE information in the CRF.

It is not acceptable for the investigator to send photocopies of the participant's medical records to GSK in lieu of completion of the GSK /AE/SAE CRF page.

There may be instances when copies of medical records for certain cases are requested by GSK. In this case, all participant identifiers, with the exception of the participant number, will be redacted on the copies of the medical records before submission to GSK.

The investigator will attempt to establish a diagnosis of the event based on signs, symptoms, and/or other clinical information. Whenever possible, the diagnosis (not the individual signs/symptoms) will be documented as the AE/SAE.

Assessment of Intensity

The investigator will make an assessment of intensity for each AE and SAE reported during the study and assign it to 1 of the following categories:
 

Mild: An event that is easily tolerated by the participant, causing minimal discomfort and not interfering with everyday activities.

Moderate: An event that causes sufficient discomfort and interferes with normal everyday activities.

Severe: An event that prevents normal everyday activities. An AE that is assessed as severe should not be confused with an SAE. Severe is a category utilized for rating the intensity of an event; and both AE and SAE can be assessed as severe.

 
An event is defined as 'serious' when it meets at least 1 of the predefined outcomes as described in the definition of an SAE, NOT when it is rated as severe.

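### Section 7.2 halts dosing for two similar moderate AEs but, as worded, not for one moderate and one similar severe AE

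*Protocol*

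**What the plan says.** Section 7.2 lists the events that stop ongoing dosing at a dose level and start a safety review:

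- first bullet: a drug-related SAE in at least one participant given active drug;
- second bullet, on moderate events: "Two similar AEs of moderate intensity in 2 or more participants";
- third bullet, on severe events: "Two AEs of severe intensity (but not necessarily similar) in 2 or more participants";
- fourth bullet: a sentinel rule, which refers back to these criteria for a sentinel on active drug.

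After a halt, dosing "may resume only following approval of a substantial amendment by the MHRA as well as the ethics committee".

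Section 10.3.3 has three intensity grades (mild, moderate, severe). For each AE the investigator must "assign it to 1 of the following categories". The same section warns that severe does not mean serious.

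Section 7.1.4 withdraws individuals: "Any participant who experiences an AE of moderate or severe intensity that is considered attributable to dosing with GSK3882347".

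The timing differs between the parts. In Part 1 (section 1.3, Table 2), "Approximately 15 minutes will be observed between the dosing of the remaining participants", and each period has a single dose. In Part 2 (section 1.1), dosing is daily for seven days and staggered: "Dosing of the remaining eight participants (seven active and one placebo) in that cohort will occur at least 120 hours later". The data that the Dose Escalation Committee (DEC) must see before escalating are, under section 9.5.1, "Part 2: Up to Day 8 (24 hours post-Day 7) for safety and PK".

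**The concern.** A stopping rule should not become easier to pass as events get worse. Here it does. Two moderate headaches in two participants stop the dose level. If one of them is severe instead, the pair contains only one moderate and only one severe event, so neither criterion is met.

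The case is foreseeable. Gastrointestinal toxicity is the only risk of the investigational product listed in section 2.3.2, and section 7.1.1 sets moderate diarrhea at 4 to 6 extra stools per day and severe at 7 or more. Two participants at +6 stop dosing. One at +6 and one at +7 do not, unless the second is also a related SAE.

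What is lost is the automatic halt, with the safety review and the amendment requirement that follow it. In Part 1 the effect is small, because the remaining participants receive one dose each within a short time. In Part 2 the other participants have daily doses ahead of them, and the data required for the escalation decision are complete only after the last dose.

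**Working it through.** The protocol states no operating characteristic for section 7.2, so there is no figure to reproduce. The check is on the logic of the rule, followed by a count of the doses exposed.

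**Step 1: the rule as written.** For one kind of AE, let M be the number of participants with a moderate event and S the number with a severe event. No participant counts in both, because each event has one category. Leaving aside related SAEs, dosing halts if M >= 2 (second bullet) or S >= 2 (third bullet).

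| Participants with similar AEs of at least moderate intensity | Patterns (M = moderate, S = severe) | Patterns with no halt |
|---|---|---|
| 2 | MM halt; **MS no halt**; SS halt | 1 of 3 |
| 3 | MMM, MMS, MSS, SSS all halt | 0 of 4 |
| 4 | all halt | 0 of 5 |

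With three or more events in two categories, at least two share a category, so the gap is confined to exactly two cases. These are counts of patterns, not frequencies.

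**Step 2: the rule with the second bullet widened.** Dosing halts if M + S >= 2 for similar events, or if S >= 2. At two, three or four cases no pattern is missed. Among pairs, only the similar MS pair changes. Pairs with a mild event, and dissimilar moderate-plus-severe pairs, give no halt under either wording.

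**Step 3: doses exposed in one Part 2 cohort.** Inputs from section 1.1: 8 non-sentinel participants (7 active, 1 placebo) and 7 daily doses. Assume that the mixed pair arises among these 8, is known after their Day d dose, and both affected participants are withdrawn. Then 8 - 2 = 6 continue, and the doses left are 6 x (7 - d). If both affected participants were on active drug, 7 - 2 = 5 of the six are on active, which leaves 5 x (7 - d) active doses.

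| d | All doses left | Active doses left (both affected on active) |
|---|---|---|
| 1 | 6 x 6 = 36 | 5 x 6 = 30 |
| 3 | 6 x 4 = 24 | 5 x 4 = 20 |
| 5 | 6 x 2 = 12 | 5 x 2 = 10 |
| 7 | 0 | 0 |

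The sentinels are left out. They start at least 120 hours earlier, so they have at most one dose left after the others take their Day 1 dose. Section 1.1 allows that interval to be changed on emerging PK data.

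**Step 4: scale under assumed rates only.** The protocol gives no AE rates. Suppose that one kind of non-serious AE is moderate with probability a and severe with probability b, independently in n active participants. The chance of ending with exactly one of each and no others is n(n - 1) x a x b x (1 - a - b)^(n - 2).

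| n | a, b (assumed) | Halt as written | Mixed pair | Halt after the change |
|---|---|---|---|---|
| 8 | 10%, 5% | 23.7% | 10.6% | 34.3% |
| 8 | 20%, 10% | 61.3% | 13.2% | 74.5% |
| 8 | 30%, 10% | 81.5% | 7.8% | 89.4% |
| 6 | 10%, 5% | 14.5% | 7.8% | 22.4% |
| 6 | 20%, 10% | 43.6% | 14.4% | 58.0% |
| 6 | 30%, 10% | 65.0% | 11.7% | 76.7% |

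First row: 8 x 7 x 0.10 x 0.05 x 0.85^6 = 10.6%. Nothing in the protocol supports severe rates this high, so the conclusion does not rest on this table.

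**The case against.** The strongest reply is that *moderate* was meant as at least moderate. A severe event, which prevents everyday activities, also does what the moderate definition describes. The Amendment 2 rationale treats severe as the stricter tier, for which similarity is waived, so nobody intended a worse event to cancel a halt. That may well be the intent, but the text does not say it. Categories are assigned one per event, and section 7.1.4 names both grades when both are meant. If the intent was at least moderate, the edit makes the text agree with it.

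Second, the sentinel bullet might be read as stopping the cohort on a single qualifying event in the active sentinel, since one person cannot meet a two-participant criterion. This is arguable. Even so, it leaves pairs among the other participants uncovered.

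Third, other safeguards exist. Section 7.1.1 interrupts or discontinues drug for diarrhea, section 7.1.4 withdraws affected participants, section 7.3 lets the investigator withdraw anyone for safety, section 8 requires immediate discussion of safety concerns with the sponsor, and section 9.5.1 gives the DEC ongoing monitoring. It is fair to say that these make it unlikely that everyone else would simply carry on, and that the dose counts are therefore ceilings. But they act on individuals or rest on judgment, and the fixed DEC review comes after the last Part 2 dose. None is a mandatory halt of the dose level.

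Fourth, the second and third bullets require neither relatedness nor active treatment, so a wider rule could halt dosing for unrelated or placebo events. That cost is real, but it already applies to two similar moderate events.

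**Conclusion.** The concern holds on the text. With exactly two similar AEs, one moderate and one severe, and no related SAE on active treatment, section 7.2 forces no halt, while the milder moderate pair does. Until a third similar case or a DEC review, stopping the other participants depends on the judgment of the investigator, the sponsor or the DEC.

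The gap is narrow and falls mainly on Part 2, where at most 36 further doses in a cohort (30 of them active if both affected participants were on active drug) are left without a stopping rule, falling to none by Day 7. That ceiling assumes the pair is among the non-sentinel participants, both are withdrawn, and nobody intervenes. The conclusion also assumes that the Dose Escalation Plan, which is not at hand, does not already settle the reading. It should be fixed, because a mandatory rule in a first-in-human study ought not to give a weaker response to a worse pattern.

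**What to change.** In the second bullet of section 7.2, insert *or severe* after *moderate*, so that two similar AEs in two or more participants trigger the halt whichever of the two grades each has. Leave the third bullet as it is, since it still covers dissimilar severe events. If the Dose Escalation Plan repeats the rule, align it.

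The cost is one phrase, plus an occasional additional halt whose reversal needs a substantial amendment approved by the regulator and the ethics committee.
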